9.1 Adverse Events

Definitions and procedures for recording, evaluating, follow-up, and reporting of AEs are provided in Appendix 11. The intensity of AEs will be graded in the following manner:

| | | |
|-----------|-----------|---|
| Absent: | • Grade 0 | • No AE |
| Mild: | • Grade 1 | • An event that is easily tolerated by the subject, causing minimal discomfort and not interfering with everyday activities. |
| Moderate: | • Grade 2 | • An event that causes sufficient discomfort to interfere with normal everyday activities. |
| Severe: | • Grade 3 | • An event that prevents normal everyday activities. An AE that is assessed as severe should not be confused with a SAE. Severe is a category utilized for rating the intensity of an event; and both AEs and SAEs can be assessed as severe. |

Solicited AEs will be collected on the day of vaccination and the 7 subsequent days (Days 1-8) and the intensity grading will be applied (Table 9.1 and Table 9.2). By definition, all local solicited symptoms are considered related to vaccination.

Unsolicited AEs will be collected on the day of vaccination and the 28 subsequent days (Days 1-29).

Table 9.1 Intensity Grading for Solicited Local AEs (Days 1 to 8)

| AE | Grade | Definition |
|-------------------------|-------|--|
| Pain at injection site* | 0 | Absent |
| | 1 | Does not interfere with activity |
| | 2 | Interferes with activity and/or repeated use of non-narcotic pain reliever >24 hours |
| | 3 | Prevents daily activity and/or repeated use of narcotic pain reliever |
| Redness* | 0 | ≤2.5 cm |
| | 1 | 2.5 – 5 cm |
| | 2 | 5.1 – 10 cm |
| | 3 | >10 cm |
| Swelling* | 0 | ≤2.5 cm |
| | 1 | 2.5 – 5 cm and does not interfere with activity |
| | 2 | 5.1 – 10 cm or interferes with activity |
| | 3 | >10 cm or prevents daily activity |
| Itching | 0 | Absent |
| | 1 | Mild, no interference with normal activity |
| | 2 | Moderate, some interference with normal activity |
| | 3 | Significant, prevents normal activity |

*FDA toxicity grading scale [25].

Table 9.2 Intensity Grading* for Solicited Systemic AEs (Days 1 to 8)

| AE | Grade | Definition |
|---------------------|--------------|--|
| Fever | 0 | <38°C |
| | 1 | ≥38 – 38.4°C |
| | 2 | ≥38.5 – 38.9°C |
| | 3 | ≥39°C |
| Headache | 0 | Absent |
| | 1 | Mild, no interference with normal activity |
| | 2 | Moderate, some interference with normal activity and/or repeated use of non-narcotic pain reliever >24 hours |

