The occurrence of AEs (serious and non-serious) will be assessed by non-directive questioning of the subject at each visit. AEs volunteered by the subject during or between visits as subject diary card entries or detected through observation, physical examination, laboratory test, or other assessments during the entire trial, will be documented. Subjects will be instructed that they must immediately report any AEs with serious symptoms, subjective complaints or objective changes in their well-being to the investigator or the clinic personnel, regardless of the perceived relationship between the event and the test vaccine.

SAEs, MAAEs and AEs leading to trial or vaccine withdrawal will be collected up to 12 months after the last dose administration. After Visit 15 (Month 12), only SAEs and MAAEs that according to the investigator are considered to be related to study vaccination will be collected.

Intercurrent medical conditions and AESIs will be collected throughout the trial.

Clinical laboratory testing for safety evaluations are provided in Appendix 6. Definitions and procedures for recording, evaluating, follow-up and reporting of AEs are provided in Appendix 11.

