9.4.15 Visit 13 (Day 91)

The following procedures will be performed during Visit 13:

- Physical examination (including weight and general condition).
- Safety assessments (SAEs, intercurrent medical conditions, AEs leading to trial or vaccine withdrawal, AESIs and MAAEs, concomitant medications and vaccinations).
- Blood draw for:
 - Safety laboratory (~9 ml).
 - Immunogenicity – VNTs (~18 ml), IgM/IgG/IgA (~6 ml), PBMCs* for CMI (~40 ml), immune receptor sequencing (5 ml).

* PBMCs will be taken for a subset of the first 5 subjects in Group 2 and all subjects in Groups 1, 3 and 4.

9.4.16 Visit 14 (Month 6: Day 181 [1-dose groups]/ Day 209 [2-dose groups and Group 1 (Rabipur[®])]

9.4.16.1 Visit 14

The following procedures will be performed during Visit 14:

- Safety assessments (SAEs, intercurrent medical conditions, AEs leading to trial or vaccine withdrawal, AESIs and MAAEs, concomitant medications and vaccinations).
- Blood draw for:
 - Safety laboratory (~9 ml).
 - Immunogenicity – VNTs (~18 ml), IgM/IgG/IgA (~6 ml), PBMCs* for CMI (~40 ml), immune receptor sequencing (5 ml).

* PBMCs will be taken for a subset of the first 5 subjects in Group 2 and all subjects in Groups 1, 3 and 4.

In case Visit 14 cannot take place on site due to the public health emergency related to COVID-19, safety information should be collected via a phone call within the protocol-allowed time interval for Visit 14 (± 14 days).

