[REDACTED]
[REDACTED]
[REDACTED]
[REDACTED]

- In rare circumstances and in the absence of email or facsimile equipment, notification by telephone is acceptable with a copy of the SAE data collection tool sent by overnight mail or courier service.
- Initial notification via telephone does not replace the need for the investigator to complete and sign the SAE report form within the designated reporting time frames.
- The “**initial SAE report**” should be as complete as possible, including causality assessment, details of the current illness and (S)AE, the reason why the event was considered serious; date of onset and end date (if applicable); diagnostic procedures and treatment of the event; relevant medical history and concomitant medication and vaccinations; and action taken with trial vaccine. The SAE report form must be signed by the investigator or his authorized designee(s).
- Investigator must inform [REDACTED] about AESIs and cases of overdose by applying the same timelines and rules of SAEs reporting.

Determination of Expectedness, Reference Safety Information

- Expectedness will be determined by [REDACTED] according to the designated Reference Safety Information (RSI) provided in the current IB. Any updates or substantial amendments will be considered accordingly.

Observation Period

- For the purpose of this trial, the period of observation for collection of AEs extends from the time the subject gives informed consent until the end of the trial.
- All AEs that occur in the course of the clinical trial regardless of the causal relationship should be monitored and followed up until the outcome is known or it is evident that no further information can be obtained.
- There must be documented reasonable attempts to obtain follow-up information and outcome.
- It is the responsibility of the investigator to ensure that any necessary additional therapeutic measures and follow-up procedures are performed.

Post-Trial Events

- If the investigator becomes aware of any SAE that occurred after the end of the trial but is considered to be caused by the trial vaccine(s), this must be reported to [REDACTED].
- These SAEs will be processed by [REDACTED]. Instructions for how to submit these SAEs will be provided in a handout in the Investigator Site File.

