11.2.2 Unsolicited Adverse Events

Serious AEs, intercurrent medical conditions, AEs leading to trial or vaccine withdrawal, AEs of special interest (AESIs) and MAAEs will be collected by the investigator in the eCRF throughout the trial.

AEs with a suspected potential immune-mediated disease etiology will be considered AESIs. The investigator will assess if an AE is an AESI. A list of AESIs is provided in Appendix 10 of the protocol.

AEs that are reported as related to the test vaccine will be considered trial vaccine-related; missing classifications concerning trial vaccine relationship will also be considered trial vaccine-related.

Every unsolicited AE will be assigned to a vaccination dose (number) by consideration of the period of 28 days after vaccination administration. Unsolicited AEs can be assigned to either day 1 to 28 (dose 1 for any vaccination group), or day 29 to 57 (dose 2 for 2-dose regimens or dose 3 for the Rabipur group). For the Rabipur group, vaccination dose 2 is administered 8 days after vaccination dose 1, therefore no assignment of unsolicited AEs to vaccination dose 2 is done for the Rabipur group.

All AE summaries will be restricted to those AEs that occurred after the first administration of the trial product. Any other AE (ie, AE starting after trial entry and before the first vaccination) will be reflected only in the data listings. If it cannot be determined whether the AE occurred after the first administration of the trial product due to a partial onset date, then it will be counted as such. Verbatim terms in the eCRFs will be mapped to preferred terms (PTs) and system organ classes (SOCs) using the Medical Dictionary for Regulatory Activities (version 21.0 or higher).

The occurrence of unsolicited AEs reported on the day of vaccination and the 28 subsequent days will be presented. In addition selected AE summary tables will be repeated for unsolicited AEs occurring at any time after the first administration of the trial product.

Each AE summary will be displayed by vaccination group and dose regimen. Summaries by vaccination dose (number) will also be provided for all AEs. Summaries that are displayed by SOC and PT will be ordered by descending order of incidence of SOC and PT within each system organ class. Summaries will display number and percentage of subjects with at least 1 event and the number of events by vaccination group.

Summaries of the following types will be presented:

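### The protocol gives conflicting collection periods for ordinary unsolicited AEs, so the SAP's trial-long unsolicited-AE tables mix full early with selective late ascertainment

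*Protocol*

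**What the plan says.** Two places in the protocol point to collection over the whole trial. Appendix 11, under Observation Period, says that "the period of observation for collection of AEs extends from the time the subject gives informed consent until the end of the trial" and adds that "All AEs that occur in the course of the clinical trial regardless of the causal relationship should be monitored and followed up". Section 9.2 says that "The occurrence of AEs (serious and non-serious) will be assessed by non-directive questioning of the subject at each visit" and that AEs "detected through observation, physical examination, laboratory test, or other assessments during the entire trial, will be documented".

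Other places point to a short period. Section 9.1 says "Unsolicited AEs will be collected on the day of vaccination and the 28 subsequent days (Days 1-29". In Table 2.1 the row for unsolicited AEs cites sections 9.4.3 to 9.4.14, that is Visit 3 (Day 1) to Visit 12 (Day 57). Visit 12 is the last visit whose safety list names unsolicited AEs. The lists for Visits 13 to 15 read "Safety assessments (SAEs, intercurrent medical conditions, AEs leading to trial or vaccine withdrawal, AESIs and MAAEs, concomitant medications and vaccinations". At Visits 16 and 17 the list narrows again, in line with section 9.2, under which after Month 12 "only SAEs and MAAEs that according to the investigator are considered to be related to study vaccination will be collected". AESIs and intercurrent medical conditions continue to trial end.

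SAP 11.2.2 opens by naming SAEs, intercurrent medical conditions, AEs leading to withdrawal, AESIs and MAAEs as collected throughout the trial. It then says that "selected AE summary tables will be repeated for unsolicited AEs occurring at any time after the first administration of the trial product". Tables 14.3.1.3.1 and 14.3.1.3.2 have rows for all and for related unsolicited AEs over the duration of the trial; 14.3.1.3.3 to 14.3.1.3.5 count all of them by SOC and PT.

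**The concern.** The AEs at issue are those in none of the special categories: not serious, not medically attended, not AESIs, not intercurrent medical conditions and not a cause of withdrawal. A site could drop them 28 days after the last dose, drop them at Day 57, or go on recording them to Month 24, and cite protocol text each time.

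The trial-long tables then add together an early period in which such events are sought and a long later period in which they may appear only if a subject happens to mention them. The footnote to these tables says which days are displayed, not which events were being collected on those days. A reader who sees few ordinary AEs after Day 57 could take this as evidence that a first-in-human product causes no late events, when they may simply not have been asked about.

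**Working it through.** The plan gives no figure to reproduce. The check sets the passages side by side and counts days.

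| Source | Period for ordinary unsolicited AEs |
|---|---|
| Appendix 11, Observation Period | Consent to end of trial |
| Section 9.2 | Each visit; documented during the entire trial |
| Section 9.1 | Day of vaccination plus 28 days |
| Table 2.1 and Visits 3 to 12 | To Day 57, all groups |
| Visits 13 to 17 | Not listed |
| SAP 11.2.2, opening | Not named among events collected throughout |
| SAP 14.3.1.3.x footnotes | Day of vaccination and all later days (display only) |

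**Inputs.** Month 24 is Day 729 for all groups (Table 2.1 notes). CV7202 is given on Day 1, or on Days 1 and 29; Rabipur on Days 1, 8 and 29 (Table 8.1). In Groups 3 and 4, 8 of 16 subjects receive a second dose (section 8.5).

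**Share of Days 1 to 729 with systematic collection.**
- Section 9.1, one dose: Days 1 to 29, 29/729 = 4.0%, leaving 729 − 29 = 700 days.
- Section 9.1, two doses or Rabipur: Days 1 to 57, 57/729 = 7.8%, leaving 729 − 57 = 672 days. The visit lists give the same 57 days for every group.
- Appendix 11: all 729 days.

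So for 672 to 700 of the 729 tabulated days, the tables rest either on full AE collection or on the special categories only, depending on the passage followed. Within that, SAEs and MAAEs are limited to related ones for the last 729 − 365 = 364 days (one dose) or 729 − 393 = 336 days (two doses and Rabipur).

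**Window length by table column, under section 9.1.**
- Regimen columns, as in 14.3.1.3.2: 57/29 = 1.97.
- Dose-level columns, as in 14.3.1.3.1 and 14.3.1.3.3: the 1 µg and 2 µg columns average (8 × 29 + 8 × 57)/16 = 43 days. The 5 µg column has 29 and Rabipur 57. Rabipur against 1 or 2 µg is 57/43 = 1.33; Rabipur against 5 µg is 1.97.
- 14.3.1.3.4 shows only one-dose groups and 14.3.1.3.5 only groups dosed on Day 29, so the window is equal across columns within each.

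**Days 30 to 57 in one-dose subjects.** The visit lists still name unsolicited AEs, but the Dose 1 diary is collected at Visit 8 (Day 29), later diaries are tied to CV7202 Dose 2 or Rabipur Dose 3, and Visit 9 is only for Groups 1, 3a and 4a. Collection to Day 57 is therefore less intensive for these subjects.

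**The case against.** The best defence is that the operational text is coherent. The endpoints, section 9.1, the diary rules, Table 2.1 and the visit lists all point to dosing plus 28 days with assessment up to Visit 12, and SAP 11.2.2 names what continues afterwards. On that view the trial-long rows mean in-window AEs plus later special categories. This is a sensible reading, but neither document states it, and section 9.2 supports Appendix 11, so the latter is not a stray sentence. Intercurrent medical conditions are also not defined in the supplied text, which leaves open how many ordinary late events enter by that route.

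The defence is right on impact. The primary endpoint for unsolicited AEs covers Days 1-29 and has its own tables, 14.3.1.2.1 to 14.3.1.2.7. The trial-long tables are additional and descriptive, and listing 16.2.7.1.1 shows start and end dates.

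Some stronger readings are tempting but unsupported:
- That no collection period is defined. Several are defined, and they conflict.
- That all dose columns differ two-fold in collection time. This holds only under section 9.1, and only between regimens or for 5 µg against Rabipur. Unequal windows follow from per-dose collection and also occur in the 28-day any-dose tables.
- That differences between columns will reflect site practice. The documents do not show how sites recorded late AEs, and the annotated eCRF and data management plan are not available here.
- That Days 1 to 57 could serve as one uniform period for all groups. The diary and Visit 9 rules contradict that.

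**Conclusion.** The conflict stands in current text, and SAP section 12 does not resolve it. Its effect is confined to the trial-long unsolicited-AE tables, where systematic collection of ordinary AEs may cover 4.0%, 7.8% or 100% of the 729 days. It does not reach the primary Day 1-29 analysis. It is worth correcting because the misreading it invites, late silence taken as late safety, is easy to prevent. The day counts assume the planned dosing days and a last visit on Day 729, ignoring visit windows. Whether late counts are in fact depressed depends on what the sites recorded, which the documents do not show.

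**What to change.** In the protocol, replace the single observation period in Appendix 11, and the matching sentences in section 9.2, by collection periods for each event type that agree with section 9.1, Table 2.1 and the visit lists. The SAP reports that all 53 vaccinated subjects had already been observed to Day 57 at the second interim analysis. For the early period this therefore records which rule applied; it does not change collection.

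In SAP 11.2.2 and tables 14.3.1.3.x:
- Separate AEs with onset inside the ordinary unsolicited-AE window from later ones.
- Present the later part by the categories collected then: SAEs, MAAEs, AESIs, intercurrent conditions and withdrawal AEs to Month 12; related SAEs, related MAAEs, AESIs and intercurrent conditions after that. Align the opening sentence of 11.2.2 with this.
- Show any other late AE, including related ones, as incidentally reported. Dropping the related row would hide reported events in a first-in-human trial.
- Footnote the windows, stating that one-dose subjects have no unsolicited-AE diary after Day 29 and that regimen columns differ in length (29 against 57 days under section 9.1).

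The cost is one protocol clarification and slightly more table work. No new data are needed.

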Appendix 12 Contraceptive Guidance and Collection of Pregnancy Information

Contraceptive Guidance

Females of childbearing potential must use acceptable methods of birth control from 2 weeks before the first administration of the test vaccine until 3 months following the last administration. The following methods of birth control are acceptable when used consistently and correctly:

- combined (estrogen and progestogen containing) hormonal contraception associated with inhibition of ovulation (oral, intravaginal or transdermal);
- progestogen-only hormonal contraception associated with inhibition of ovulation (oral, injectable or implantable);
- intrauterine devices (IUDs);
- intrauterine hormone-releasing systems (IUSs);
- bilateral tubal occlusion;
- vasectomized partner;
- sexual abstinence (periodic abstinence [e.g., calendar, ovulation, symptothermal and post-ovulation methods] and withdrawal are not acceptable).

Males must use reliable forms of contraception (condom) from the moment of the first administration of the test vaccine until 3 months following the last administration and must refrain from sperm donation from the moment of the first administration of the test vaccine until 3 months after the last administration.

Refer to the Clinical Trial Facilitation Group (CTFG) recommendations on contraception and pregnancy testing for further details [23].

Reporting and Follow-up of pregnancies

Pregnancy is an exclusion criterion for enrolment in this trial, but subjects could potentially become pregnant during their active participation in this trial.

Any pregnancy in a subject having received a trial vaccine must be reported to [REDACTED] within 24 hours of the site learning of its occurrence, using a pregnancy reporting form. If the subject becomes pregnant during the trial, she will not receive any further doses of any sponsor-supplied trial vaccine. The pregnancy must be followed to determine outcome, including spontaneous or voluntary termination, details of birth, and the presence or absence of any birth defects, congenital abnormalities, or maternal and/or newborn complications. This follow-up should occur even if the intended duration of safety follow-up for the trial has ended.

The trial site should maintain contact with pregnant subjects to obtain pregnancy outcome information.

Any complications during pregnancy (e.g., gestational diabetes or eclampsia) are to be considered as an AE; however, these complications could result in the event being an SAE. Spontaneous abortions, fetal death, stillbirth and congenital anomalies reported in the baby are always considered as SAEs. The pregnancy by itself will not be processed as an SAE. The investigator will follow the subject until completion of the pregnancy and must assess the outcome in the shortest possible time but not

more than 30 days within completion of the pregnancy. The investigator should notify [REDACTED] of the outcome of the pregnancy by submitting a Follow-up Pregnancy Report.

Appendix 13 Data Management and Quality Control

Case report forms

In this study, all clinical data (including, but not limited to, AE/SAEs, concomitant medications/vaccines, medical history, and physical assessments) will be entered onto eCRFs in a timely fashion (on the visit day during the staggered enrolment phase and within 5 days post-visit for all other visits) by the investigator and/or the investigator's dedicated site staff. All data entered into the eCRF must be verifiable against source documents at the trial site. Any changes to the data entered into the electronic data capture system will be recorded in the audit trail.

The investigator will maintain adequate and accurate records for each subject entered into the trial. Source documents such as hospital, clinic or office charts, laboratory reports, trial worksheets, and signed informed consent documents are to be included in the investigator's files along with subject trial records.

The sponsor or the CRO will check eCRF entries against source documents according to the guidelines of GCP. The consent form will include a statement by which subjects allow the sponsor or designee, as well as authorized regulatory agencies, to have direct access to source data that support data of the eCRF (e.g., subject medical files, appointment books, original laboratory records, etc.). The sponsor or designee, bound by secrecy, will not disclose subject identities or personal medical information.

Quality control

A monitor from the CRO will supervise the trial. The trial monitor will contact the investigator regularly to discuss the progress of the trial and to check the trial documents including the informed consent forms for completeness and consistency.

The trial monitor or representative of the sponsor will cross-check the data entered in the eCRF with the source data at the trial site in order to verify adherence to the trial protocol.

The eCRF will be checked for completeness and correctness by the monitor and data management department of the CRO according to the CRO's standard operating procedures (SOPs). The investigator will resolve any queries.

Trial site monitoring visits

Monitoring visits to the trial site will be made periodically during the trial to ensure that:

- The rights and well-being of human subjects are protected
- The reported study data are accurate, complete and verifiable from the source documents and
- The conduct of the trial is in compliance with the current approved protocol/amendment(s), GCP and applicable regulatory requirements.

The investigator and/or trial staff must make source documents for subjects enrolled in this trial available for inspection by CureVac AG or its designee at the time of each monitoring visit and sponsor audits, when applicable. These documents must also be

available for inspection, verification and copying, as required by regulators, by officials of the regulatory health authorities and/or IECs.

All aspects of the trial and its documentation will be subject to review by the sponsor or designee, including but not limited to the Investigator's Site File, trial vaccine, pharmacy records, subject medical records, informed consent documentation, and review of eCRFs and associated source documents. It is important that the investigator and other trial personnel are available during the monitoring visits and that sufficient time is devoted to the process.

Audits

The trial site also may be subject to quality assurance audits by the sponsor or designees. In this circumstance, the sponsor-designated auditor will contact the site in advance to arrange an auditing visit. The auditor may ask to visit the facilities where laboratory samples are collected, where the vaccine is stored and prepared, and any other facility used during the trial. In addition, there is the possibility that this trial may be inspected by regulatory agencies, including those of local (EU-EMA) or foreign governments (e.g. US-FDA and others). If the trial site is contacted for an inspection by a regulatory body, the sponsor should be notified immediately. The investigator and institution guarantee direct access for quality assurance auditors and inspectors to all trial documents and source data.

